6.8 Investigational product administration and treatment compliance

The administration of all study drugs (including investigational products) should be recorded in the appropriate sections of the CRF.

The IP (benralizumab) and influenza vaccine will be administered at the study center on treatment visits and within visit windows as specified in Table 2.

Before IP administration

Prior to each IP administration and administration of influenza vaccine:

- Investigator/authorized delegate will assess injection sites as per standards of medical care
- For WOCBP, urine pregnancy test will be done; IP will be administered only when the result of the test is negative (see Section 5.2.4.1)

IP and influenza vaccine administration

The IP and influenza vaccine will be administered by the Investigator/authorized delegate. It is advised that the site of injection of the IP be rotated such that the patient receives IP at a different anatomical site at each treatment visit. Suggested injection site rotation sequence is presented below (see Figure 3). At Week 8, the influenza vaccine should be injected at a site different than that of the IP injection site and should be administered prior to IP. The injection site(s) must be recorded in the source documents and the eCRF at each treatment visit.

Figure 3 Injection sites and rotation scheme

Further details on IP administration are provided in the IP Handling Instruction. IP administration must be carried out in line with the Instruction.

After influenza vaccine administration

After influenza virus administration, the patient should be observed for a minimum of 15 minutes for the appearance of any acute drug reaction and prior to administration of IP.

After IP administration

After IP administration the patient should be observed for a minimum of 2 hours for the appearance of any acute drug reactions.

Conditions requiring IP administration rescheduling

If any of the following occur, the Investigator should reschedule the visit and the IP should not be administered until the rescheduled visit:

- The patient has an intercurrent illness, that in the opinion of the Investigator may compromise the safety of the patient in the study (eg, viral illnesses)
- The patient is febrile ($\geq 38^{\circ}$ C; $\geq 100.4^{\circ}$ F) within 72 hours prior to the IP administration

6.9 Management of investigational product-related reactions

Appropriate drugs (eg, epinephrine, H1 and H2 antihistamines, and corticosteroids), and medical equipment to treat acute anaphylactic reactions must be immediately available. Study personnel must be trained to recognize and treat anaphylaxis (Kroger et al 2011, Lieberman et al 2010). Management of anaphylaxis must be in accordance with current standard of care and clinical guidelines. Details on anaphylaxis management are provided in Appendix F.

Anaphylaxis will be defined as a serious reaction that is rapid in onset and may cause death (Simpson et al 2006). Anaphylaxis typically manifests as 1 of 3 clinical scenarios:

- 1. The acute onset of a reaction (minutes to hours) with involvement of the skin, mucosal tissue, or both, and at least 1 of the following: a) respiratory compromise or b) reduced blood pressure or symptoms of end-organ dysfunction
- 2. Two or more of the following that occur rapidly after exposure: involvement of the skin/mucosal tissue, respiratory compromise, reduced blood pressure or associated symptoms and/or persistent gastrointestinal symptoms
- 3. Reduced blood pressure after exposure

Patients will have had a pre-assessment (ie, vital signs and lung function) prior to IP administration) and should be observed after IP administration for a minimum of 2 hours for the appearance of any acute drug reactions. Patients should also be observed in the clinic for 15 minutes after vaccine administration.

In order to help understand the potential drug-relatedness of any acute reaction, a blood sample should be drawn as close as possible to the event for possible additional ADA testing (if not already scheduled for this visit). Serum tryptase or other blood or urine testing relevant to the diagnosis of anaphylaxis may be obtained at a local lab at the discretion of the Investigator.

7. SAFETY REPORTING

7.1 Adverse events

The Principal Investigator is responsible for ensuring that all staff involved in the study are familiar with the content of this section.

7.1.1 Definition of adverse events

An adverse event (AE) is the development of an undesirable medical condition or the deterioration of a pre-existing medical condition following or during exposure to a pharmaceutical product, whether or not considered causally related to the product. An undesirable medical condition can be symptoms (eg, nausea, chest pain), signs (eg, tachycardia, enlarged liver) or the abnormal results of an investigation (eg, laboratory findings, ECG). In clinical studies, an AE can include an undesirable medical condition occurring at any time, including run-in or washout periods, even if no study treatment has been administered.

The term AE is used to include both serious and non-serious AEs.

7.1.2 Definitions of serious adverse event

A serious adverse event (SAE) is an AE occurring during any study phase (ie, screening/run-in, treatment, washout, follow-up), that fulfills 1 or more of the following criteria:

- Results in death
- Is immediately life-threatening
- Requires in-patient hospitalization or prolongation of existing hospitalization
- Results in persistent or significant disability/incapacity or substantial disruption of the ability to conduct normal life functions
- Is a congenital abnormality or birth defect
- Is an important medical event that may jeopardize the patient or may require medical intervention to prevent any of the outcomes listed above

For further guidance on the definition of a SAE, see Appendix B.

7.1.3 Recording of adverse events

7.1.3.1 Time period for collection of adverse events

All AEs, including SAEs, will be collected from the time the patient, parent, or legal guardian signs the informed consent/assent throughout the treatment period and including the follow-up period (through Week 20).

7.1.3.2 Follow-up of unresolved adverse events

Any AEs that are unresolved at follow-up in the study will be followed up by the Investigator for as long as medically indicated, but without further recording in the CRF. AstraZeneca retains the

right to request additional information for any patient with ongoing AE(s)/SAE(s) at the end of the study, if judged necessary.

The requirement to follow-up AEs is not intended to delay database lock or production of the Clinical Study Report (CSR). These activities should proceed as planned with ongoing AEs if necessary.

Any follow-up information of ongoing SAEs after database lock will be reported to AstraZeneca.

7.1.3.3 Variables

The following variables will be collect for each AE

- AE (verbatim)
- The date when the AE started and stopped
- Maximum intensity of the AE
- Whether the AE is serious or not
- Investigator causality rating against the IP (yes or no)
- Action taken with regard to IP
- AE caused patient's withdrawal from study (yes or no)
- Outcome.

It is important to distinguish between serious and severe AEs. Severity is a measure of intensity whereas seriousness is defined by the criteria in Section 7.1.2. An AE of severe intensity need not necessarily be considered serious. For example, nausea that persists for several hours may be considered severe nausea, but not a SAE. On the other hand, a stroke that results in only a limited degree of disability may be considered a mild stroke but would be a SAE.

7.1.3.4 Causality collection

The Investigator will assess causal relationship between IP and each AE, and answer 'yes' or 'no' to the question 'Do you consider that there is a reasonable possibility that the event may have been caused by the investigational product?'

For SAEs causal relationship will also be assessed for other medication and study procedures. Note that for SAEs that could be associated with any study procedure the causal relationship is implied as 'yes'.

A guide to the interpretation of the causality question is found in Appendix B.

7.1.3.5 Adverse events based on signs and symptoms

All AEs spontaneously reported by the patient or reported in response to the open question from the study personnel: 'Have you had any health problems since the previous visit/you were last asked?', or revealed by observation will be collected and recorded in the CRF. When collecting

AEs, the recording of diagnoses is preferred, when possible, to recording a list of signs and symptoms. However, if a diagnosis is known and there are other signs or symptoms that are not generally part of the diagnosis, the diagnosis and each sign or symptom will be recorded separately.

7.1.3.6 Adverse events based on examinations and tests

The results from protocol mandated laboratory tests and vital signs will be summarized in the CSR. Deterioration as compared with baseline in protocol-mandated laboratory values and vital signs should therefore only be reported as AEs if they fulfill any of the SAE criteria or are the reason for discontinuation of treatment with the IP.

If deterioration in a laboratory value/vital sign is associated with clinical signs and symptoms, the sign or symptom will be reported as an AE and the associated laboratory result/vital sign will be considered as additional information. Wherever possible, the reporting Investigator will use the clinical, rather than the laboratory term (eg, anemia versus low hemoglobin value). In the absence of clinical signs or symptoms, clinically relevant deteriorations in non-mandated parameters should be reported as AE(s).

Any new or aggravated clinically relevant abnormal medical finding at a physical examination as compared with the baseline assessment will be reported as an AE.

7.1.3.7 Symptoms of the disease under study

When collecting AEs, the recording of diagnoses is preferred, when possible, to recording a list of signs and symptoms. Asthma symptoms or signs, such as wheeze, cough, chest tightness, dyspnea, breathlessness and phlegm, will be recorded as AEs only when:

- The sign or symptom is serious according to definitions, see Section 7.1.2
- The patient discontinues the study due to the sign or symptom
- The sign or symptom is new to the patient or not consistent with the patient's pre-existing asthma history (defined as within 1 year of Visit 1) as judged by the Investigator.

7.1.4 **Hy's Law**

Cases where a subject shows elevations in liver biochemistry may require further evaluation and occurrences of AST or ALT $\ge 3x$ ULN together with total bilirubin $\ge 2x$ ULN may need to be reported as SAEs. Refer to Appendix D for further instruction on cases of increases in liver biochemistry and evaluation of Hy's Law.

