3.6 Discontinuation from investigational product

Patients will be discontinued from IP in the following situations:

- 1. Patient decision. The patient is free to discontinue treatment at any time, without prejudice (see Section 3.7)
- 2. Adverse event (AE) that in the opinion of the Investigator or Sponsor contraindicates further dosing
- 3. Risk to patient as judged by the Investigator or AstraZeneca
- 4. Eligibility requirement found not to be fulfilled (see Section 3.4). Risk to patient as judged by the Investigator or AstraZeneca.
- 5. Severe non-compliance with study protocol
- 6. Pregnancy
- 7. Lost to follow-up¹
- 8. Development of any study specific criteria for discontinuation:

¹ Patient is considered lost to follow up when any of the following attempts of contact are failed: 3 attempts of either phone calls, faxes or emails; having sent one registered letter/certified mail; or one unsuccessful effort to check the vital status of the patient using publicly available sources, if allowed by local regulations.

- (a) Anaphylactic reaction to the investigational product requiring administration of epinephrine
- (b) Development of helminth parasitic infestations requiring hospitalization
- (c) An asthma-related event requiring mechanical ventilation

All patients who prematurely discontinue investigational product should return to the study center and complete the procedures described for the Premature IP Discontinuation (IPD) visit within 4 weeks ± 3 days.

The reasons for premature discontinuation of IP should be recorded in the eCRF.

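### Under section 7.1.3.7, a familiar, non-serious asthma symptom that ends dosing is not an AE if the patient stays in the study

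*Protocol*

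**What the plan says.** Section 7.1.3.7 restricts AE recording for symptoms of the disease under study. Wheeze, cough, dyspnea and similar signs "will be recorded as AEs only when" one of three conditions is met:

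- First, seriousness: the event meets a criterion of section 7.1.2.
- Second, leaving the study: "The patient discontinues the study due to the sign or symptom".
- Third, novelty, which the investigator judges against the asthma history within 1 year of Visit 1: "The sign or symptom is new to the patient or not consistent with the patient's pre-existing asthma history".

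Section 7.1.3.6 sets the corresponding rule for protocol-mandated laboratory values and vital signs. Deterioration in these should "only be reported as AEs if they fulfill any of the SAE criteria or are the reason for discontinuation of treatment with the IP". The same section, and section 5.2.1, also require a new or aggravated physical examination finding to be reported as an AE when it is clinically relevant (7.1.3.6) or clinically significant in the investigator's judgment (5.2.1).

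Section 3.6 lists the reasons for stopping IP. One is "Adverse event (AE) that in the opinion of the Investigator or Sponsor contraindicates further dosing". Others are patient decision and risk to the patient. The reason for stopping must be entered in the eCRF.

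**The concern.** The second trigger in 7.1.3.7 depends on leaving the study, not on stopping treatment. In this protocol the two differ, so a symptom can matter enough to end dosing and still not qualify as an AE. AEs are the first endpoint listed under the safety objective (section 2.3). An event kept out of AE recording has no entry for intensity, causality, action taken with IP or outcome (section 7.1.3.3), and it does not reach the summaries by system organ class and preferred term (section 8.5.3.2). A laboratory or vital-sign deterioration with the same consequence for dosing would be recorded. Sites may also treat the same event differently, because the sections on examination findings point the other way.

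**Working it through.** No arithmetic applies. The check is to read the sections side by side and trace the rule case by case.

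**Step 1: are stopping IP and leaving the study the same thing here?** No.

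- Discontinuation of IP has its own section (3.6), separate from withdrawal from the study (3.7). Withdrawal under 3.7.2 covers both IP and assessments.
- Patients who stop IP early return for a dedicated visit (3.6, 4.2, Table 2).
- Section 7.1.3.3 collects action taken with IP and withdrawal from the study as two separate AE variables.
- Sections 8.3.2 and 8.5 keep patients in the analysis after premature discontinuation of IP.

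A patient who is off IP but still in the study is therefore a state the protocol provides for.

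**Step 2: apply 7.1.3.7 to an asthma symptom that leads to stopping IP.**

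| Case | Symptom | Patient leaves the study? | AE under 7.1.3.7? |
|---|---|---|---|
| a | Serious | Either | Yes, first trigger |
| b | New, or inconsistent with history | Either | Yes, third trigger |
| c | Non-serious, consistent with history | Yes | Yes, second trigger |
| d | Non-serious, consistent with history | No | No trigger applies |

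Only case d falls through, and it does so because of the stated restriction, not because a detail was left open.

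**Step 3: does other data collection replace the missing AE record?** Only in part.

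- Exacerbations are counted by arm on the safety set (8.5.3.1), but section 5.3.2 requires systemic corticosteroids, hospitalization or an emergency department visit. A milder worsening that ends dosing is not one.
- The eCRF reason for stopping IP (3.6) keeps a trace of the event, but not the AE variables of 7.1.3.3 or a coded term for the AE tables.
- The asthma-specific stopping criterion in 3.6, "An asthma-related event requiring mechanical ventilation", would be expected to meet a seriousness criterion, so it belongs to case a and does not help with case d.

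**Step 4: compare with the neighbouring AE rules.**

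- For laboratory values and vital signs, the trigger in 7.1.3.6 is that they "are the reason for discontinuation of treatment with the IP". For asthma symptoms it is leaving the study. The protocol gives no reason for the difference.
- A complete physical examination, which includes the respiratory system, is scheduled at the premature discontinuation visit (Table 2, 5.2.1.1). If known wheeze is found there to be clinically relevantly worse than at baseline, 5.2.1 and 7.1.3.6 make it an AE. Under 7.1.3.7 the same non-serious, familiar wheeze is not an AE while the patient stays in the study. The protocol does not say which section prevails.

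**The case against.** The strongest reply is that the remaining gap is small and partly covered. The third trigger is left to the investigator, who could reasonably judge that a worsening bad enough to end dosing is not consistent with the earlier history. The protocol prefers diagnoses to symptoms, so a diagnosis such as a drug reaction is not caught by the restriction. Worsened wheeze heard at the discontinuation visit has a route to AE status through the examination rule. For patients who stop early, only the discontinuation visit is expressly described, and the Week 20 visit in 4.3 is described for those who complete treatment. It is therefore unknown how many patients would be off IP and clearly still in the study.

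Most of this stands as a limit on size. It does not remove the gap: the first two routes depend on how a site classifies the event, and the examination route itself clashes with the restriction in 7.1.3.7.

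A reader might also infer more than the documents support:

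- *That asthma symptoms are AEs only if the patient leaves the study.* Serious symptoms, and new or atypical ones, are AEs either way.
- *That 7.1.3.7 contradicts the IP-stop trigger in 7.1.3.6.* That trigger governs laboratory values and vital signs, so both rules can be followed. The wording is unaligned, not contradictory.
- *That 7.1.3.7 contradicts 3.6.* Section 3.6 does not say how asthma symptoms are recorded, and it offers patient decision and risk to the patient as other reasons for stopping. A stop reason with no matching AE arises only if the site selects the AE reason.

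**Conclusion.** The point holds for case d only. A non-serious asthma sign or symptom, consistent with the patient's history, that leads to stopping IP while the patient remains in the study is not recorded as an AE under 7.1.3.7. Such events can be missing from the AE tables and from the record of action taken with IP. Separately, the restriction pulls against 5.2.1 and 7.1.3.6 on aggravated examination findings, and this needs reconciling.

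The size cannot be derived. The protocol gives no rate of IP discontinuation for asthma symptoms, and the number of affected patients is probably small. It would be tempting to conclude that AEs leading to IP discontinuation are in fact undercounted, or to attach percentage points to an assumed one or two patients among the 50 per arm. The documents support neither step: the count is unknown, and the protocol itself specifies no table of AEs leading to IP discontinuation (the SAP, not shown, may do so).

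The conclusion rests on reading the restriction in 7.1.3.7 literally and on the protocol's own separation of stopping IP from leaving the study. No planned analysis is invalidated. This is a cheap improvement of minor weight.

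**What to change.** Reword the second condition in 7.1.3.7 so that it is met when, because of the sign or symptom, the patient either stops IP or withdraws from the study. The existing items in 7.1.3.3 on action taken with IP and on study withdrawal will then separate the two, so no new variable is needed.

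In the same amendment, reconcile 7.1.3.7 with 5.2.1 and 7.1.3.6 by stating which rule prevails when an aggravated examination finding is also a familiar asthma sign. This concerns AE recording only; it changes no rule on when dosing stops.

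The cost is one phrase and one clarifying sentence in an amendment, carried into the eCRF completion instructions. The downside is that a few more AEs will be reported.

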7.1.5 Reporting of serious adverse events

All SAEs have to be reported, whether or not considered causally related to the IP, or to the study procedure(s). All SAEs will be recorded in the CRF.

If any SAE occurs in the course of the study, then Investigators or other center personnel will inform appropriate AstraZeneca representatives within 1 day, ie, immediately but **no later than 24 hours** from when he or she becomes aware of it.

The designated AstraZeneca representative will work with the Investigator to ensure that all the necessary information is provided to the AstraZeneca Patient Safety data entry site within 1 calendar day of initial receipt for fatal and life threatening events and within 5 calendar days of initial receipt for all other SAEs.

For fatal or life-threatening AEs where important or relevant information is missing, active follow-up will be undertaken immediately. Investigators or other center personnel will inform AstraZeneca representatives of any follow-up information on a previously reported SAE within 1 calendar day, ie, immediately but **no later than 24 hours** from when he or she becomes aware of it.

Once the Investigators or other center personnel indicate an AE is serious in the Web-based Data Capture (WBDC) system, an automated email alert will be sent to the designated AstraZeneca representative.

If the WBDC system is not available, then the Investigator or other study center personnel is to report a SAE to the appropriate AstraZeneca representative by telephone.

The AstraZeneca representative will advise the Investigator/study center personnel how to proceed.

The reference document for definition of expectedness/listedness is the IB for the AstraZeneca drug.

7.2 Overdose

- An overdose with associated AEs will be recorded as the AE diagnosis/symptoms on the relevant AE modules in the CRF and on the Overdose CRF module
- An overdose without associated symptoms will be reported on the Overdose CRF module only

If an overdose on an AstraZeneca study drug occurs in the course of the study, then Investigators or other center personnel will inform appropriate AstraZeneca representatives within 1 day ie, immediately but **no later than 24 hours** from when he or she becomes aware of it.

The designated AstraZeneca representative will work with the Investigator to ensure that all relevant information is provided to the AstraZeneca Patient Safety data entry site.

For overdoses associated with a SAE, standard reporting timelines apply, see Section 7.1.5. For other overdoses, reporting should be done within 30 days.

7.3 Pregnancy

All pregnancies and outcomes of pregnancy should be reported to AstraZeneca.

7.3.1 Maternal exposure

If a patient becomes pregnant during the course of the study IP should be discontinued immediately.

Pregnancy itself is not regarded as an AE unless there is a suspicion that the IP under study may have interfered with the effectiveness of a contraceptive medication. Congenital abnormalities/birth defects and spontaneous miscarriages should be reported and handled as SAEs. Elective abortions without complications should not be handled as AEs. The outcome of all pregnancies (spontaneous miscarriage, elective termination, ectopic pregnancy, normal birth, or congenital abnormality) should be followed up and documented even if the patient was discontinued from the study.

If any pregnancy occurs in the course of the study, then Investigators or other center personnel inform appropriate AstraZeneca representatives within 1 day, ie, immediately but **no later than 24 hours** from when he or she becomes aware of it.

The designated AstraZeneca representative will work with the Investigator to ensure that all relevant information is provided to the AstraZeneca Patient Safety data entry site within 1 or 5 days for SAEs (see Section 7.1.5) and within 30 days for all other pregnancies.

The same timelines apply when outcome information is available.

